6 RISK ANALYSIS

Worldwide, over 8500 treatments have been performed to date with the MR guided FUS ExAblate device. Risk analysis for InSightec ExAblate systems/clinical investigations has been conducted as part of previously approved FDA IDE submissions (G930140, G990151, G990184, G990201, G000203, G010225, G020001, G020182, G050177, G050221, G060017, G060023, G070022, G080009, G080206, G100127, G100169, and P040003 and P110039). This data has been re-examined by the study sponsor and it has been concluded that this risk analysis is applicable to the proposed clinical investigation. The key consideration here is the fact that this proposed study has the same purpose as the previous ones, namely to coagulate soft tissue within the body by means of ExAblate. Additional risks, new and unique to this study are discussed below.

The potential risks described below will be explained to the subject in the informed consent process.

6.1 Potential risks – (ExAblate):

Risk of MR Imaging

- The study subject may find the MR unit claustrophobic and request to leave the study despite pre-procedure sedation.
- MRI has no known deleterious biological effects in patients with no contraindications. The incidence of claustrophobia during MRI examinations is approximately 10-15%, although it is expected to be less frequent in the study population due to the use of sedation.
- Gadolinium DTPA (trade name: Magnevist/Omniscan) is an intravenously injectable contrast medium for MRI. The package insert notes that there are no known contraindications. Precautions should be exercised for patients with a history of grand mal seizures, severely impaired renal function or hemolytic anemia. The very unlikely possibility of a reaction, including anaphylactic or cardiovascular reactions, should be considered especially for patients with a known sensitivity to Gd or history of asthma. Adverse reactions include: headache (incidence 8.7%), localized pain, vomiting, paresthesia, and dizziness and localized warmth (incidence less than 2%). Additional adverse effects listed on the package insert occur with an incidence of less than 1%.

Risks incidental to the treatment

There is a potential risk of conscious sedation, which includes reaction to the drugs or over-sedation.

There is a potential risk from the intravenous catheter used during the treatment. Subjects can expect a small amount of pain and/or bleeding/bruising at the IV site. There is a small risk of infection. This procedure will follow the ‘standard of care’ at the Study Sites.

There is a potential risk to the patient of deep venous thrombosis from lying stationary for 3 to 4 hours. The risk to the patient from lying still for this treatment should be no greater than that of lying still for any other reason. For treatments under this protocol, it will be the surgeon discretion to provide patients with compression stockings or wraps for the period of the treatment.

There is a risk that the patient may experience a sore neck or discomfort from lying in the same position for a long time during the treatment.

Risks associated with the ExAblate treatment

- There is a potential risk of hemorrhage around the treated area during ExAblate treatment. In ExAblate thermal ablation, the high temperatures result in immediate protein denaturation and coagulative necrosis, with the result that any bleeding that might occur in the capillary bed and within small vessels would be rapidly sealed. At the end of the ExAblate procedure a contrast (Gadolinium or other MRI contrast agent) enhanced MR imaging is performed to assess the blood flow within the treated area and neighboring tissue. In addition to the repeated MR imaging during every sonication of the treatment, this final step is an independent treatment outcome assessment tool that is giving information on blood flow in the treated surroundings and could serve as a final check of tissue status. In the treatments that have been completed to date in other organs, this complication has never been observed.
- Focused ultrasound therapy involves precisely controlled pulses of acoustic energy resulting in tissue heating (typically to 65-85°C for 15 seconds), in small tissue volumes. Discrete small volumes are consecutively treated at operator controlled time intervals without significant overall heat accumulation in the body. Since the beam is localized in the treatment area, there is no significant heating effect on pain sensitive areas such as adjacent normal tissue or skin. The patient will be sedated but in constant verbal contact with the physician and appropriate action can be taken in the event that a patient does experience discomfort. Remedies could involve increasing the time interval between consecutive treatment pulses or increasing the level of anesthesia and/or analgesia. The patient also has the ability to stop the procedure at any time by activating a handheld shutdown circuit switch.
- There is a risk to the patient from improper targeting of the focal point, and ablation of an area of tissue outside the planned treatment volume. At the start of treatment, the system includes a mandatory step that requires the operator to first check the alignment of the patient anatomy, the focal point of the transducer and

the MR imaging system. This procedure is done while the patient is in position for treatment. It achieves alignment within ± 2 mm in all 3 axes. For each sonication delivered during treatment, the operator gets continuous feedback on the position of the intended treatment point superimposed on the thermal dosimetry image and can make corrections where required. The system also includes an independent safety-monitoring loop that continuously compares the physical position of the transducer to the current intended treatment point to monitor for any un-commanded motion in the system from any source. If such a move is detected, the system immediately stops the delivery of energy to the patient, and notifies the operator of the error.

- The treatment results in the necrosed tissue being left in situ to be naturally removed by the body. There is a potential risk to the patient from a reaction to the volume of treated tissue (fever or infection). This effect has been often observed in other technologies of tissue ablation such as arterial embolization, cryo-therapy or Radiofrequency ablation of other tumors but has not been observed to a significant level thus far in the clinical experience accumulated from over 8500 treatments with ExAblate.
- There is a risk to the patient that the skin can become heated to the point where a burn can occur. This heating can be caused by direct heating of the skin (improper treatment targeting), irregularities on the skin surface, or treatment of a volume of tissue too close to the skin and the conduction of sufficient heat to cause a burn at the surface. In the case of a 1° or 2° burn, the skin should heal without a scar. In the case of a 3° burn, a scar or loss of sensation in the area of the burn could result. Following several reports of skin burns in uterine fibroids treatment that occurred due to tiny air bubbles trapped in the pubic hair, investigators were instructed to shave any hair in the beam path which significantly reduced events of skin burns. No additional burns have been reported in over 30 cases of bone treatments.
- There is a risk from patient motion during a sonication, or between sonications. This could cause a movement of the tumor relative to the planned treatment volume on the system, and in extreme cases could result in the treatment of a point outside the planned treatment volume.
- There is a risk of cavitation in the tissue at the focal point. However, we believe that through proper system design, there is a very minimal risk that cavitation could occur during a treatment, even in the event of user error. We have taken extensive steps in the system design to address cavitation as a potential risk and provide two layers of protection. The first is in the design of the sonication treatment planner. This automated process takes as its input tumor depth in tissue, focal volume and tissue absorption, and based on pre-set safe operating limits selects sonication parameters that remain well below the cavitation threshold at the focal point. The system also includes a real time cavitation detection monitor. A graphic output of this system is displayed to the user during

the treatment. If cavitation is observed the user is instructed to immediately terminate the sonication before any harm would come to the patient being treated. It is not believed that a transient event of even a few seconds of cavitation could pose any medical risk to the patient

Risks associated with pathological fractures

Localized structural damage to the bone following ExAblate treatment could occur immediately following the treatment or could be delayed, resulting from death of osteocytes at and near the target zone (from the elevated temperature). No such events have been reported in the bone cases treated to date.

Although patients will be screened for possible impending fractures (section 3.2.2 Exclusion Criteria, #1 and Section 7.4), there is still a risk of fracture during the study associated with the bone metastases themselves. Thus, fractures could occur near the treated site or at the site of untreated lesions. All fractures will be captured on the adverse events CRF. Physicians will report the location of any fractures and assess their relationship to the procedure and the ExAblate device.

6.2 Anticipated Treatment Side Effects From ExAblate

Based on previous treatment experience, the following anticipated side effects have been identified as possible treatment related complications of ExAblate treatment. These can be classified into Non-significant and Significant Anticipated Treatment Side Effects based on their medical severity, additional treatment required and long term consequences for the patient. All Treatment Side Effects will be reported in the Case Report Forms for the study and included in the final study analysis.

Non-significant Anticipated Treatment Side Effects of ExAblate treatment are those, which normally resolve without sequelae within 10-14 days of the treatment:

- Transient fever
- Oral temperature $>100.4^{\circ}\text{F}/38^{\circ}\text{C}$
- Pain in the area of treatment.
- Transient pain in the skin.
- Swelling or firmness in the treated area

- Minor (1° or 2°) skin burns less than 2 cm in diameter
- Bruising in the treatment area

Significant Anticipated Treatment Side Effects of ExAblate are those which may require medical treatment, may have sequelae, and for which time of resolution is not defined:

- Necrosis of tissue outside the targeted volume due to heat conduction from heated bone.
- Nerve damage, or loss of sensation in the area other than the treatment area.
- Hemorrhage in the treated area requiring emergency treatment.
- Skin burns with ulceration of the skin.
- Skin retraction, and scar formation..
- Complications of conscious sedation (Cardiac, Pulmonary, Drug reactions)

The table below summarizes all the potential risks to a patient from ExAblate treatment and the time course when they would most likely be observed.

Immediate (up to 48 hrs post treatment)	Mid term (up to one month)	Long term (more than one month)
Pain in the treatment area.	Pain in the area of treatment	Pain in the area of treatment
Skin burns	Swelling or firmness in the treated area	Nerve damage or loss of sensation in the treated or neighboring areas
Necrosis of normal tissue resulting from incorrect targeting	Nerve damage or loss of sensation in the treated or neighboring areas	Scar formation from skin burn.
Risks of conscious sedation including reaction to drugs and over sedation.	Fever as reaction to treated tissue.	
Adverse reactions to Gadolinium DTPA		

Transient pain in skin or back	Ulceration of skin or scar formation from skin burn.	
Bleeding in the treatment area.		
Pathological fractures	Pathological fractures	Pathological fractures

The anticipated significant treatment side effects of the ExAblate treatment have an estimated combined incidence of less than 5% based on prior clinical experience in other organs.

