2.4 Study End Points

Safety

A full safety profile will be developed for the ExAblate treatment of bone metastases. All adverse events will be captured and summarized as defined in **Section-6.2**. Adverse events (type, frequency, severity) are expected to be similar to those captured for the original PMA study (PMA # P110039).

For his study, the Safety comparison with the data of the Pivotal (IDE Study G070022) study will be descriptive with no statistical endpoints.

Efficacy

A full efficacy profile will be developed for the ExAblate treatment of bone metastases. For this study efficacy will be determined by comparing outcomes at the 3 month visit to baseline within subjects. Additionally the safety and efficacy of treatment Responders and Non-Responders will be tabulated, and compared with that of the original PMA (P110039).

The primary endpoint is the proportion of responders at the 3 month study visit.

Definition of terms:

- Patient Responders: these are all ExAblate treated patients who experience at least a 2 point improvement from baseline on NRS at the treated site without increase in medications
- Patient Non-Responders: these are all ExAblate treated patients who experience less than 2 points improvement from baseline to 3 months on the NRS at the treated site without increase of medication or increased medications.
- Patient Pain Progression: these are all ExAblate treated patients who either experience 2 points worsening from baseline to 3 months on the NRS at the treated site or who increase morphine equivalence 25% or more. Pain progression is a subset of non-responders.

Secondary Endpoints

This study has two secondary end points. The goal of these secondary end points is to assess the impact of the ExAblate treatment of painful bone Mets on the overall quality of life and clinical benefits to ExAblate MRgFUS treated patients:

Quality of life outcomes of all treated patients will be captured during the course of the study. A comparison between baseline and 3 months post-ExAblate treatment of the BPI-QoL will be performed.

Pain Medications of all patients will be captured and summarized. Changes in narcotic medications will be expressed in morphine equivalents.

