4.2 Pre-Treatment Procedures

Patients potentially qualifying for the study will be offered an Informed Consent to sign prior to further evaluation. Those who accept will complete study forms. Any patients not qualifying will be exited from the study as screening failures and will not be included in the efficacy and safety analyses.

A complete medical history will be obtained to determine the patient's general health status, current symptoms, frequency and dosage of their current analgesic intake etc. Kidney and Liver function tests and coagulation profile will be performed. Baseline pain scores will be established. CT examination (with and without contrast) will also be performed.

All patients will complete a run-in period to optimize patient pain meds at baseline in relation to patient pain, functionality and pain meds side effects, during which time study questionnaires (NRS, BPI-QoL, KPS, medications) will be completed.

Pre-Treatment Procedure

1. At the end of the run-in period and in the event the CT imaging is not already available, then baseline CT examination will be performed to identify the tumor size, location and extent and device accessibility as well as to evaluate the patient's ability to cooperate during the ExAblate procedure.
2. If at this point it is determined that the patient **does not** meet all Inclusion and Exclusion criteria and cannot be treated, the patient will be exited from the study. These patients will be considered screening failures, and will not be included in any of the safety or efficacy endpoint analyses.
3. If the patient meets all study criteria, the patient may have the ExAblate treatment.
4. ExAblate-treated patients will complete follow-up visits at, 1 week, and 1, 2 and 3 months.

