4.5 Study Requirements and Visit Schedule

The tables below summarize the data that will be captured during the course of this study.

Table 1: Study Visits

	Window Allowance	Imaging	Questionnaire s	Additional Data
Enrollment	N/A	CT**	PE, NRS, BPI, KPS	Freq. and dosage of analgesics.
Run-in Visits:			NRS, BPI, KPS	Freq. and dosage of analgesics.
Visit #1 Baseline MR Imaging and ExAblate Treatment (2 nd session permitted).	On Run-in Visit 2 or within 1-week ± 3 days of Run-in	MR	NRS, BPI, KPS	Freq. and dosage of analgesics.
Visit #2 (office): 1-Week Post-Tx	± 3 days		PE, NRS, BPI, KPS	Freq. and dosage of analgesics.
Visit #3 (phone): 1-Month Post-Tx	± 1 Week		NRS, BPI, KPS	Freq. and dosage of analgesics.
Visit #4 (phone) 2-Months Post-Tx	± 2 Weeks		NRS, BPI, KPS	Freq. and dosage of analgesics.
Visit #5(office) 3-Months Post-Tx	± 2 Weeks		PE, NRS, BPI, KPS	Freq. and dosage of analgesics.
**May be completed at any visit before treatment.				

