5.3 Missing Data

Analyses will be performed on both observed and data with missing values imputed per the method of last observation carried forward (LOCF) where data for missing visits is assigned the value of the previous visit. Analyses will include the presentation of results calculated based on the intent-to-treat principle.

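### The LOCF rule in section 5.3 lets a 1-week score, taken while procedural pain may still be present, stand as the 3-month outcome, with bias possible in either direction

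*Combined protocol and SAP*

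**What the plan says.** - **Section 6.2** introduces a list of effects that "have been identified as possible treatment related complications of ExAblate treatment". The non-significant ones are those "which normally resolve without sequelae within 10-14 days of the treatment", and the list includes "Pain in the area of treatment". No incidence, severity or typical duration is given for this pain. The time-course table in the same section also places it under mid term (up to one month) and long term (beyond one month).
- **Sections 4.2 and 4.5** set the schedule: "ExAblate-treated patients will complete follow-up visits at, 1 week, and 1, 2 and 3 months". The Table 1 row "Visit #2 (office): 1-Week Post-Tx" has a window of ± 3 days. The 1-month visit has ± 1 week.
- **Section 5.3** calls for an observed-data analysis and an LOCF analysis. Under LOCF, "data for missing visits is assigned the value of the previous visit". It names no earliest visit that may be carried and does not say which analysis is primary.
- **Section 2.4** makes the 3-month responder proportion the primary endpoint. A responder improves by at least 2 points without increased medication. Progression applies to patients who "experience 2 points worsening from baseline to 3 months on the NRS at the treated site", or whose morphine equivalents rise by 25% or more.
- **Section 5.2** tests P10 (responders) against P01 (patients who worsen).
- **Section 4.4** has patients rate pain at the treated place. Nothing there or elsewhere separates procedural pain from tumour pain.

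**The concern.** The week-1 visit is the one scheduled follow-up whose whole window falls inside the period in which section 6.2 says side effects normally resolve. A value from that visit may describe recovery from the procedure rather than a durable result. LOCF can nevertheless make it the 3-month result.

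Two errors are possible. A temporary flare, or extra opioid taken to cover it, can be scored as 3-month progression and enter P01. Early relief that would not have lasted can be scored as a 3-month response and enter P10. The first mixes a safety effect into the efficacy result; the second overstates durability, which matters in a one-arm study. Planned power is only 0.70, so a few misplaced patients can change the LOCF result.

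**Working it through.** **1. Timing.** Week-1 visit: 7 ± 3 = day 4 to 10, at or before the lower end of the 10-14 day limit. The 1-month visit, taking a month as 30 days: 30 ± 7 = day 23 to 37, after that limit. Section 4.3 (step 21) allows a second session within two weeks of the first, and Table 1 does not say which session starts the follow-up clock. If it is the first, a week-1 value could precede completion of treatment.

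**2. The plan's own figure.** Inputs from section 5.2: P10 = 0.60, P01 = 0.30, one-sided α = 0.025, power 0.70, N = 65, 70 enrolled. Exact McNemar power is

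Σₘ Pr[Bin(n, P10 + P01) = m] × Pr[Bin(m, P10/(P10 + P01)) ≥ cₘ],

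where cₘ is the smallest c with Pr[Bin(m, ½) ≥ c] ≤ 0.025. This gives 0.693 at n = 65 and 0.730 at n = 70. The smallest n reaching 0.70 is 67. The stated 65 is reproduced to within two patients, so the sample size is not in question here.

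**3. Effect of carrying week 1.** The documents give neither dropout timing nor a flare rate, so both are assumed. Let w be the share of patients with week-1 data only, and f the share of those whom LOCF scores as progression because of a flare. The rest keep the planned 60/10/30 split of responders, neither, and progression.

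- Flare: P10 = 0.60(1 − wf); P01 = 0.30 + 0.70wf.
- All carried as responders: P10 = 0.60 + 0.40w; P01 = 0.30(1 − w).
- In neither cell: P10 = 0.60(1 − w); P01 = 0.30(1 − w).

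For n = 70 and w = 5%:

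| Scoring of week-1-only patients | P10 | P01 | Power |
|---|---|---|---|
| None (complete data) | 0.600 | 0.300 | 0.73 |
| All responders | 0.620 | 0.285 | 0.83 |
| In neither cell | 0.570 | 0.285 | 0.70 |
| Flare, f = 0.1 | 0.597 | 0.3035 | 0.71 |
| Flare, f = 0.5 | 0.585 | 0.3175 | 0.62 |
| All progression, f = 1 | 0.570 | 0.335 | 0.50 |

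At w = 2%, power is 0.69 for f = 0.5 and 0.64 for f = 1. If all of the plan's dropout allowance (70 − 65 = 5 patients, 7.1%) were week-1-only, power would be 0.65, 0.57 and 0.40 for f = 0.25, 0.5 and 1. The 0.83 is no real gain in power: it is what arises if early relief is counted as lasting.

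**4. One worked result.** The expected counts at n = 70 are 42 v 21, exact one-sided p = 0.0056. If five patients are week-1-only, about 3 would have been responders and 1.5 progressors. Scoring all five as progression gives 42 − 3 = 39 v 21 − 1.5 + 5 = 24.5. At 39 v 24, p = 0.0385, above 0.025. With the five in neither cell the counts are 39 v 19 or 20, p = 0.006 or 0.009.

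**The case against.** A reader might infer that section 6.2 expects 10 to 14 days of pain, that the week-1 score is therefore known to be transient, and that LOCF turns procedural pain into progression and so biases the test against the device. The documents do not support that reading.

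- Section 6.2 names a possible effect with an upper limit on its usual duration. Pain may be gone by day 4, and the table in 6.2 also allows it beyond one month.
- A flare counts as progression only at 2 points worsening or a 25% rise in morphine equivalents. A smaller flare gives a non-responder outside P01. A patient with baseline NRS 9 or 10 cannot worsen by 2 points.
- Week-1 responders are carried forward too, so the direction of bias is unknown.
- The affected group must miss months 1, 2 and 3. Section 4.4 allows phone visits, section 7 requires three contact attempts and a certified letter, and life expectancy under 3 months is an exclusion.
- The observed-data analysis is untouched.

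All of this stands and limits the claim. It does not close the path, because section 5.3 has no earliest eligible visit. Nor can the LOCF result be treated as merely supportive, since neither analysis is named primary. Early loss is also plausible: section 5.4 describes the population as terminally ill.

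A further fair objection concerns the remedy. Taking every week-1-only patient out of P01 would discard real early progression and could favour the device. That is why the opposite bound must be reported with it.

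**Conclusion.** The gap is real but limited. Followed as written, the plan can make a score and medication level from day 4 to 10 stand as the 3-month responder or progression outcome, and no provision prevents it. Only the LOCF analysis is affected, and only for patients with nothing after week 1.

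Neither the direction nor the size of the bias can be established from the documents. The 0.50 to 0.83 range rests on an assumed 5% of week-1-only patients and on extreme scoring at each end. With few such patients and few flares, power moves by only a point or two. The change is worth making because it is cheap and the planned power leaves little margin.

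**What to change.** Amend section 5.3 to state that:

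1. NRS, morphine-equivalent and BPI-QoL values recorded within 14 days of the last ExAblate session are not carried to month 3. Tying the rule to dates rather than visit names also covers a second session. The 14 days follows the upper end of the range in section 6.2 and is a convention, since the table there allows later pain.
2. Patients with no later value count as non-responders in the responder proportion.
3. The P10-versus-P01 test is reported under both bounds: these patients in neither cell, and all of them in P01.
4. These results appear beside the observed-data analysis and the LOCF analysis as now written.
5. One of these analyses is named primary.

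The cost is a few sentences and a few extra result rows. The restricted LOCF result may rest on slightly fewer patients or be somewhat less favourable. No visit or clinical procedure changes.
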